## **TYPE OF ANALYSIS**

This document describes the primary statistical analysis for SMART-C study in accordance with protocol version 2.0.

### **Data Safety and Monitoring Board (DSMB) Analysis**

This study has a DSMB to review the progress and safety of the study. The DSMB will conduct an interim safety and adherence analysis when the first 75 participants have either reached post-treatment week 12 or dropped out of the study. Additional meetings may be considered by the DSMB at a frequency commensurate with the risk as determined by the DSMB.

### **Primary analysis: Post-treatment week 12**

The analysis for the primary endpoint, SVR12, will be conducted after all participants have completed the post-treatment week 12 visit or prematurely discontinued from study. All the safety and efficacy data through to the post-treatment week 12 visit will be cleaned, finalised, and included for the analysis.

## **GENERAL CONSIDERATIONS FOR DATA ANALYSES**

### **Statistical Methods**

Analysis results will be presented using descriptive statistics. For categorical variables, the number (n) and percentage of participants in each category will be presented. For continuous variables, the number of participants (n), mean and standard deviation (SD), median, interquartile range (IQR, Q1-Q3), range (minimum, maximum) will be reported; for inclusion in the manuscript, an appropriate determination will be made depending on the variable, size and distribution of the population studied. Statistical tests will be 2-sided and performed at the 5% significance level, unless specified. For the analysis of categorical outcomes, Chi-squared tests or exact equivalents (for small numbers) will be used. For comparison of continuous measures, t tests or non-parametric equivalents will be used as appropriate for the observed data distribution.

For the primary analysis of non-inferiority, the percentage of participants achieving SVR12 in each arm and the difference in percentages of participants achieving SVR12 between study arms will be calculated with confidence intervals using the normal approximation to the binomial distribution.

Non-inferiority of the 8-week regimen of glecaprevir/pibrentasvir with a simplified monitoring strategy to the 8-week regimen of glecaprevir/pibrentasvir with a standard monitoring strategy with regard to the proportion achieving SVR12 will be shown if the lower bound of the confidence interval for the differences is above the non-inferiority margin of -6 percentage points.

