## 1.0 Background and rationale

Chronic hepatitis C virus (HCV) treatment was interferon-based for two decades, with the addition of ribavirin (RBV), Pegylated interferon (PEG-IFN), and initial protease inhibitor direct acting antiviral (DAA) therapies (telaprevir, boceprevir) providing stepwise improvements in the rate of sustained virological response (SVR). Despite these improvements in interferon-containing regimens, treatment uptake remained low in most countries, ranging from <1% to a maximum of 5% of people with chronic HCV initiating therapy each year.

Fortunately, recent years have seen a revolution in HCV therapeutic development, in particular the interferon-free direct acting antiviral (DAA) regimens. Short, simple (once daily dosing oral regimens), highly tolerable, short-duration (8-12 weeks) therapy with pangenotypic potency and extremely high efficacy (cure rates above 95%) will soon be the norm. The broad implementation of such therapeutic regimens has the potential to produce one of the major turnarounds in disease burden seen in public health and clinical medicine.

The capacity to scale-up interferon-free DAA therapy would be enhanced by simplified treatment monitoring strategies. The “next generation” DAA regimen of glecaprevir (300mg)/pibrentasvir (120mg), a protease inhibitor and NS5A inhibitor, provides key features for HCV treatment simplification, including on-treatment monitoring: 1) pangenotypic activity with extremely high efficacy (SVR>95%); 2) no relationship between time to undetectable HCV RNA and SVR; 3) minimal drug-related toxicity; 4) ease of dosing (three pills once daily); and short duration (8 weeks in non-cirrhosis and 12 weeks in cirrhosis for treatment naïve patients). In phase II and III clinical trials in patients without cirrhosis, 8 weeks of glecaprevir (300mg)/pibrentasvir (120mg) has provided intention-to treat SVR rates of 99.1%, 98%, 97%, and 93.1% in genotype 1, 2, 3, and 4-6 populations, respectively with extremely low rates of drug-related toxicity.

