## **10.0 Statistics**

### **10.1 Sample Size**

The study is designed to enrol a total of 375 patients: 125 in the standard arm and 250 in the simplified arm. The primary efficacy endpoint of SVR12 will be assessed within each arm, and the primary comparison of SVR12 rates will be for non-inferiority of standard to simplified arms. With these patient numbers, the study has approximately 80% power to show non-inferiority to standard treatment monitoring with a lower confidence bound for the difference (standard – simplified) in SVR12 rates greater than –6% (assuming an SVR12 rate of 96% in both arms).

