**Figure 1 Study Schema**

**Sample size and power**

The study was designed to enrol a total of 375 participants with genotype 1-6 HCV infection who had not received previous HCV treatment and did not have cirrhosis, randomised 2:1 - 250 participants in the simplified monitoring arm and 125 participants in the standard monitoring arm.

With these participant numbers and under the assumption that the proportion achieving SVR12 would be 96% in both arms, the study would have approximately 80% power to show non-inferiority of the simplified monitoring strategy to the standard monitoring strategy, with a lower confidence bound for SVR12 in the standard monitoring arm greater than 90% or with a lower confidence bound for the difference (simplified arm minus standard arm) in SVR12 greater than -6%. The 90% threshold for non-inferiority of the eight weeks glecaprevir/pibrenatasvir with standard monitoring was based on the clinical trial data available at the time of study design (SVR12 96%), minus a 6% non-inferiority margin. The non-inferiority margin of 6 percentage points was selected in accordance with the principles outlined in guidance on conducting non-inferiority trials; the choice of margin ensured minimal to no loss of efficacy.

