## STUDY ENDPOINTS

**Table 9. Study endpoints and outcomes**

Primary endpoint	Non-inferiority of simplified on-treatment monitoring to standard on-treatment monitoring (ITT population)	Included in primary analysis
Secondary endpoints	Non-inferiority of simplified on-treatment monitoring to standard on-treatment monitoring (mITT population)	Included in primary analysis
	Non-inferiority of simplified on-treatment monitoring to standard on-treatment monitoring (per-protocol population)	Included in primary analysis
	Virologic failure	Included in primary analysis
	On-treatment adherence	Included in primary analysis
	Early treatment discontinuation	Included in primary analysis
	SVR12, by genotype	Included in primary analysis
	SVR12, by HIV serostatus	Included in primary analysis
	Adverse events	Included in primary analysis
	Laboratory abnormalities	Included in primary analysis
	Unscheduled clinic visits	Included in primary analysis
	Change from baseline in patient reported outcome summary measures	Included in primary analysis
	Presence of baseline polymorphisms	Included in primary analysis
	Presence of treatment-emergent substitutions in patients with virologic failure	Included in primary analysis
Additional pre-specified outcomes	Cost-effectiveness	Not included in primary analysis
	Health practitioner acceptability	Included in primary analysis

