**Table 11. Treatment outcome, ITT population**

Outcome	Standard monitoring (N=XXX)	Simplified monitoring (N=XXX)	Difference between arms (95% CI)	P
SVR12, n (%)				
Virologic failure, n (%) On-treatment failure (non-response, breakthrough) Post-treatment relapse		NA NA	NA NA	
Failure for other reasons, n (%) Discontinuation Loss to follow up or missing SVR12 data				

\*Analysis tables will also be presented for the mITT, mITT-VF and PP populations

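### The normal-approximation interval for the SVR12 difference undercovers when true SVR12 is 96–99%, lopsidedly against simplified monitoring; the non-inferiority decision is sound at the planned 96%

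*SAP*

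**What the plan says.** The SAP, Statistical Methods, sets the interval for the primary analysis: "the difference in percentages of participants achieving SVR12 between study arms will be calculated with confidence intervals using the normal approximation" to the binomial. Non-inferiority is shown "if the lower bound of the confidence interval for the differences is above the non-inferiority margin of -6 percentage points". Protocol 10.5 also specifies the normal approximation for the SVR12 percentages in the non-inferiority analyses. Neither document says whether the variance is pooled or a continuity correction applied. The 95% level comes from protocol 10.3 and the SAP table headings.

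Two provisions for small numbers stand nearby, but neither covers this interval. The exact equivalents in Statistical Methods are alternatives to chi-squared tests. The exact 95% intervals under Secondary efficacy endpoints are by arm, genotype and HIV serostatus.

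SAP Tables 10 and 11 print the between-arm difference with its 95% CI beside a P value. Their footnotes repeat the tables for the mITT, mITT-VF and per-protocol populations. SAP Table 9 lists non-inferiority in the mITT and per-protocol populations as secondary endpoints.

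The design has "125 in the standard arm and 250 in the simplified arm" (protocol 10.1) and assumes that "the proportion achieving SVR12 would be 96% in both arms" (SAP, Sample size and power). The protocol background cites "SVR rates of 99.1%, 98%, 97%, and 93.1% in genotype 1, 2, 3, and 4-6 populations".

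**The concern.** Few failures are expected in the smaller arm: 125 × 0.04 = 5 at the planned 96%, and 125 × 0.01 = 1.25 at 99%. An unpooled interval estimates each arm's variance from that arm's own observed rate. When the standard arm happens to have very few failures, its variance is underestimated; with none, it is set to zero and that arm's uncertainty drops out. Those are also the trials in which the standard arm looks best, so the interval is narrowest when the estimate is most unfavourable to simplified monitoring.

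The reported difference and its 95% CI are therefore at stake. A reader could take an interval wholly below zero as evidence that simplified monitoring is worse when the strategies are equal. At rates close to 100%, the non-inferiority rule could also become too easy to pass.

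**Working it through.** **Inputs.** n = 125 standard and 250 simplified; SVR12 96% in both arms; margin −6 points; two-sided 95% interval; difference = simplified − standard (SAP, Primary efficacy endpoint). The variance formula is an assumption: unpooled, without continuity correction.

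**1. The plan's own power.** The SAP states "approximately 80% power to show non-inferiority of the simplified monitoring strategy".
- SE = √[0.96 × 0.04 × (1/125 + 1/250)] = 0.02147.
- Power = Φ(0.06/0.02147 − 1.96) = Φ(0.835) = 79.8%.
- Standard-arm size for 80% power at 1:2: (1.96 + 0.8416)² × 0.96 × 0.04 × 1.5 / 0.06² = 125.6, so 126 against the planned 125.

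The stated power is reproduced with one-sided 2.5% and unpooled variance. A one-sided 5% level would give 87.5%.

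**2. The interval under test.** With observed proportions p₁ (simplified) and p₀ (standard):

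(p₁ − p₀) ± 1.96 √[p₁(1 − p₁)/250 + p₀(1 − p₀)/125].

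The operating characteristics below come from full enumeration of the two binomial distributions.

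**3. Equal arms (true difference 0), % of trials.**

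| True SVR12 | Planned: coverage | Planned: CI wholly below 0 | Planned: CI wholly above 0 | Score: CI wholly below 0 | Score: CI wholly above 0 |
|---|---|---|---|---|---|
| 96% | 93.8 | 4.8 | 1.4 | 1.9 | 2.9 |
| 97% | 93.0 | 5.7 | 1.3 | 1.8 | 2.8 |
| 98% | 91.6 | 7.3 | 1.1 | 1.2 | 3.0 |
| 98.5% | 90.9 | 8.2 | 0.9 | 0.6 | 3.3 |
| 99% | 92.5 | 6.9 | 0.5 | 0.1 | 3.9 |

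Each tail is nominally 2.5%. Score means the Miettinen-Nurminen interval, whose coverage over these rows is 95.2–96.1%. The planned lower-side excess is 4.8/2.5 = 1.9 times nominal at 96%. It is at least twice nominal from about 96.3% to 99.2% and peaks at about 3.3 times. By 99.5% the tail has fallen to 2.0%.

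**4. Non-inferiority error (true loss of exactly 6 points), % of trials passing the rule.**

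| True standard/simplified SVR12 | Planned rule | Score |
|---|---|---|
| 96/90 | 2.15 | 2.6 |
| 98/92 | 2.3 | 2.5 |
| 99/93 | 2.9 | 2.2 |
| 99.5/93.5 | 3.9 | 1.9 |
| 100/94 | 6.4 | 1.6 |

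The planned rule passes 2.5% at a standard-arm SVR12 of about 98.6%.

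**5. Particular results (failures, standard v simplified).**
- 0/125 v 4/250: difference −1.6 points; SE = √(0.984 × 0.016/250) = 0.00794; CI −3.16 to −0.04, which excludes zero. Fisher P = 0.31 and uncorrected chi-squared P = 0.16. Score interval −4.05 to +1.41.
- 0/125 v 0/250: the planned CI is 0 to 0; the score interval is about −1.5 to +3.0.
- 5/125 v 14/250: planned lower limit −6.06 (fails), score −5.94 (passes).
- 0/125 v 9/250: planned lower limit −5.91 (passes), score −6.70 (fails).

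The chance of no standard-arm failure is 0.96¹²⁵ = 0.6%, 0.98¹²⁵ = 8% and 0.99¹²⁵ = 28%.

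**The case against.** A reader might infer that the primary non-inferiority test is anti-conservative. The documents do not support that. At the design rate its error is 2.15%, and the score interval's is higher (2.6%). The primary set is ITT with missing counted as failure, which lowers SVR12. The source rates also include 93.1% for genotypes 4–6, and those genotypes are eligible. The 6.4% figure needs a standard arm at exactly 100%.

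The other objections, and what stands of each:
- **The lower-side excess concerns the upper limit, which the decision rule does not use.** True. It cannot create a false non-inferiority claim; the fault is in the reported interval.
- **The adjacent P value protects the reader.** Partly. With equal arms at 96–99%, chi-squared gives P < 0.05 against simplified monitoring in only 0.1–1.9% of trials. But a CI and a P value that disagree in one table row are themselves a defect.
- **Unpooled variance is inferred.** True, and material. With pooled variance, both errors stay below 2.5% at the rates checked (96–99.5%). With a continuity correction, the lower-side tail is 2.7% at 96–97% and non-inferiority error is at most 2.0% up to 99.5%. The unpooled reading is the usual one and matches the stated power, but the SAP should settle it.
- **Other populations.** The SAP ties the normal approximation to the primary analysis and does not say which method gives the difference CI in the mITT, mITT-VF and per-protocol tables. Its use there is an inference.
- **Verdicts seldom differ.** Planned and score verdicts disagree in 1.5% of trials at equal 96%, 0.14% at equal 99% and 0.5% at 96/90.

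**Conclusion.** The point holds as a fault of interval coverage. If the SAP's normal approximation means the unpooled interval, the 95% CI for the difference covers 90.9–93.8% when the arms are equal at 96–99%. Most of the error falls on the side that makes simplified monitoring look worse (4.8–8.2% against 2.5%).

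The primary non-inferiority decision is sound at the planned 96%. Its error exceeds 2.5% only from a standard-arm SVR12 of about 98.6%. Such rates are more likely in the mITT and per-protocol repeats, which remove some or all missing-as-failure cases, than in the ITT analysis.

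This rests on 125/250 participants analysed, the 95% level and the unpooled reading. The change should be made, but it does not call the design or the primary test into question.

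**What to change.** In SAP Statistical Methods, name the interval for the SVR12 difference as the two-sided 95% Miettinen-Nurminen score interval, simplified minus standard. Use it for the non-inferiority rule (lower limit above −6 points) and for every between-arm difference column in Tables 10 and 11, in all four populations. Margin, direction and sample size are unchanged.

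The cost is one sentence in the SAP and a standard software option. Exact power at 96% is 83.3% with the planned rule and 83.7% with the score interval. At a true 97% it falls from 92.7% to 91.3%, and at 98% from 98.7% to 97.1%. One-sided non-inferiority error becomes about 2.6% at 96/90. With equal arms at 96–99%, the tail in favour of simplified monitoring is 2.8–3.9%. These costs are small beside the coverage regained, but they should be accepted knowingly.

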### **10.5 Definition of Intent-to-treat Population**

Intent-to-treat (ITT) and modified intent-to-treat (mITT) populations will be used for efficacy analyses. All patients who receive at least one dose of study drug will be included in the ITT population (and safety population). The mITT population will exclude patients who have completed treatment (>95% adherence) (according to phone contact at week 8), but have not returned for their SVR12 assessment. The data from the ITT and mITT will be presented by the treatment arm assigned at the time of randomisation. For the primary analyses of non-inferiority tests, the percentage of patients achieving SVR12 in each arm will be calculated with confidence intervals (CI) using the normal approximation to the binomial distribution.

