### Primary efficacy endpoint

The primary efficacy endpoint is sustained virologic response at week 12 post treatment (SVR12), defined as plasma HCV RNA below the lower limit of quantitation (<10 IU/mL; target not detected [TND] or target detected, not quantifiable [TDnq]) at 12 weeks after the last dose of study drug in the ITT population.

The Aptima HCV Quant Dx assay, version 2.15.5 will be used to measure HCV RNA (Hologic, Inc., Marlborough, MA, USA). The LLOQ for this assay is 10 IU/mL.

The primary efficacy endpoint of SVR12 will be assessed within each arm, and the primary comparison of SVR12 will be for non-inferiority of the simplified monitoring arm compared to the standard monitoring arm (simplified arm minus standard arm).

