### **Secondary efficacy endpoints**

Secondary efficacy endpoints include:

- Proportion of participants achieving SVR12 in each arm (in the mITT, mITT-VF and per-protocol populations);
- Proportion of participants with virological failure;
- Proportion of participants who are adherent to treatment and study visits (on-treatment adherence and early treatment discontinuation);

For virological endpoints, the point estimates and 95% exact confidence intervals will be reported by study arm, by HCV genotype and by HIV serostatus.

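### The per-arm SVR12 confidence intervals in the primary analysis use the normal approximation with about five expected failures in the standard arm, and cover 87.6% instead of 95% at the planned 96%

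*SAP*

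**What the plan says.** The SAP (Statistical Methods) covers both the SVR12 percentage in each arm and the difference between arms; for the primary analysis these "will be calculated with confidence intervals using the normal approximation to the binomial distribution". Protocol 10.5 says of the per-arm figure: "the percentage of patients achieving SVR12 in each arm will be calculated with confidence intervals (CI) using the normal approximation to the binomial distribution".

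The per-arm figures are planned primary output. SAP, Primary efficacy endpoint: "The primary efficacy endpoint of SVR12 will be assessed within each arm".

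Two other places bear on the point. SAP, Secondary efficacy endpoints: "For virological endpoints, the point estimates and 95% exact confidence intervals will be reported by study arm, by HCV genotype and by HIV serostatus". SAP, Sample size and power, describes the power in terms of the -6 point margin for the difference or, alternatively, "with a lower confidence bound for SVR12 in the standard monitoring arm greater than 90" per cent.

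The SAP gives no confidence level beside the normal-approximation sentence. I take 95%, from Protocol 10.3 and from the SAP's general rule: "Statistical tests will be 2-sided and performed at the 5% significance level, unless specified".

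**The concern.** The normal-approximation interval for a single proportion works poorly when failures are few. It is centred on the observed rate and symmetric, although the sampling distribution near 100% is skewed. It therefore sits too high and is too short. Its upper limit can pass 100%, and it shrinks to zero width when an arm has no failures.

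The error falls on the limit readers care about. The lower limit for an arm tells them how low the cure rate under that monitoring strategy could plausibly be, and this method sets it too high too often. In addition, SVR12 in the ITT set would carry one kind of interval and SVR12 in the mITT, mITT-VF and per-protocol sets another, so neighbouring tables would not be comparable. If the 90% standard-arm bound were ever used as a criterion, the choice of interval could decide whether it is met.

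The concern is confined to the per-arm intervals. It is not that the difference interval is materially wrong.

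**Working it through.** **Inputs.** Standard arm n = 125, simplified arm n = 250, SVR12 96% in both arms, margin -6 points, power about 80% (SAP, Sample size and power). Two-sided 95%, z = 1.96.

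**The plan's own figure.** SE = √[0.96 × 0.04 × (1/125 + 1/250)] = 0.02147. Power = Φ(0.06/0.02147 − 1.96) = 79.8%, which agrees with the stated 80%. The design is therefore read correctly.

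**Expected failures.** 125 × 0.04 = 5; 250 × 0.04 = 10.

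**Coverage in the standard arm at a true 96%.** For x successes, p̂ = x/n and the limits are p̂ ± 1.96 √[p̂(1 − p̂)/n].

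- x = 123: 0.984 − 1.96 √(0.984 × 0.016/125) = 0.984 − 0.022 = 0.962, so the lower limit is already above 0.96.
- x = 113: the upper limit is 0.9556, below 0.96.
- The interval contains 0.96 only for x = 114 to 122.

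Under Binomial(125, 0.96):

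- P(X ≥ 123) = 0.0818 + 0.0317 + 0.0061 = 12.0%, where the lower limit is too high (nominal 2.5%).
- P(X ≤ 113) = 0.45%, where the upper limit is too low (nominal 2.5%).
- Coverage is 87.6%.

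**Other true rates.** Coverage of the normal-approximation interval, with all three methods averaged over a fine grid from 94% to 99%:

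| | 95% | 96% | 97% | 98% | 99% | Average | Exact, average | Wilson, average |
|---|---|---|---|---|---|---|---|---|
| n = 125 | 94.2 | 87.6 | 88.7 | 91.6 | 71.4 | 89.0 | 97.6 | 95.6 |
| n = 250 | 92.7 | 93.1 | 93.4 | 87.3 | 91.5 | 91.9 | 96.9 | 95.3 |

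The exact interval never falls below 95%. The upper end of this range is relevant because Protocol 1.0 cites SVR of 99.1%, 98% and 97% for genotypes 1, 2 and 3 (and 93.1% for genotypes 4 to 6).

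**Degenerate limits, standard arm.** The upper limit exceeds 100% in 25% of trials at a true 96% and 46% at 97%. Zero width occurs in 0.6% of trials at 96%, 2.2% at 97% and 8.0% at 98%.

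**Intervals at the expected counts.**

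| | Normal approximation | Exact |
|---|---|---|
| 120/125 | 92.6 to 99.4 | 90.9 to 98.7 |
| 240/250 | 93.6 to 98.4 | 92.8 to 98.1 |

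The lower limit moves by 1.7 and 0.8 points.

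**The 90% standard-arm bound, if it were used.**

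| | Lower limit above 90% from | Pass probability, true 90% (nominal 2.5%) | Pass probability, true 96% |
|---|---|---|---|
| Normal approximation | 118/125 | 6.0% | 87.1% |
| Exact | 120/125 | 1.1% | 61.6% |

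At 118 or 119 successes the method alone decides. At a true 96% those two counts have a combined probability of 87.1 − 61.6 = 25.5%.

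**The difference interval, for context.** Enumerating all 126 × 251 outcomes with the simplified arm exactly 6 points lower, the one-sided error is 2.15%, 2.27%, 2.46% and 2.90% at standard-arm rates of 96%, 98%, 98.5% and 99% (nominal 2.5%). Exact power at 96% in both arms is 83.3%.

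**The case against.** The strongest reply is that no decision depends on these intervals. Non-inferiority is judged on the difference against -6 points, and the per-arm figures are descriptive. That stands, and it limits the weight of the point. The interval is nonetheless labelled 95%, forms part of the primary output, and does not have that coverage.

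A second reply is that 96% happens to fall at a dip. Standard-arm coverage is 91.9% at 95.5% and 93.1% at 96.5%, and over a lower range of 90% to 96% it averages 92.4% (n = 125) and 93.7% (n = 250). Lower rates are possible because missing counts as failure. This is a fair caution against quoting 87.6% alone, but every one of these values is below 95%, and the shortfall grows towards the rates the protocol cites.

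Third, the exact intervals appear under the secondary endpoints, in a section that names the mITT, mITT-VF and per-protocol sets and not the ITT primary endpoint. Read narrowly, nothing contradicts. I accept this: it is an ambiguity over whether ITT SVR12 counts as a virological endpoint, and it shows that the method is already in the plan.

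Fourth, the 90% bound appears only in the sample-size text, not in the decision rule, so the figures for it are conditional. That also stands.

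Fifth, the difference interval itself covers only 93.8% at 96% in both arms and 91.6% at 98% in both arms, yet it is to be kept. The reason is that its error at the margin, which drives the decision, is close to nominal.

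Finally, preferring exact to Wilson is partly taste. Exact over-covers (98.2% at n = 125 and 96%), while Wilson covers 96.5% with a mean width of 7.2 points against 7.6. Wilson would be defensible; exact has the advantage of agreeing with the rest of the SAP.

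**Conclusion.** The point holds. The per-arm intervals prescribed for the primary analysis do not deliver their nominal coverage at the planned sample sizes and rate. Coverage is 87.6% in the standard arm and 93.1% in the simplified arm at 96%, and averages 89.0% and 91.9% over 94% to 99%. The misses fall almost wholly on the lower limit, which overstates how well the cure rate in each arm is secured.

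The consequence is moderate. Reported intervals change and the non-inferiority conclusion does not, so this should be corrected but does not put the trial's main result at risk. The figures assume 125 and 250 analysed participants, a 95% level, and normal-approximation limits that are not cut off at 100%. Cutting them off would remove impossible upper limits but would not improve coverage.

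**What to change.** In the SAP (Statistical Methods) and Protocol 10.5, name separate methods for the two quantities. For example:

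> SVR12 in each arm will be reported with a two-sided exact (Clopper-Pearson) 95% CI. The difference (simplified minus standard) will be reported with a two-sided 95% CI based on the normal approximation.

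In the SAP (Sample size and power), state whether the 90% standard-arm bound is a decision criterion. If it is, base it on the same exact interval; if not, remove it or label it as background.

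The cost is one sentence in each document plus that clarification. Standard software suffices, and neither the data nor the non-inferiority rule changes. At a true 96% the mean per-arm width rises from 6.7 to 7.6 points (n = 125) and from 4.8 to 5.2 points (n = 250), and the exact interval is somewhat conservative. If the 90% bound is kept as a criterion, its power at 96% is 61.6% instead of 87.1%, so the stated power of about 80% would not apply to it.
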